Diabetes mellitus	1	250.xx 357.2, 362.0, 366.41	E08311, E08319, E083211, E083212, E083213, E083219, E083291, E083292, E083293, E083299, E083311, E083312, E083313, E083319, E083391, E083392, E083393, E083399, E083411, E083412, E083413, E083419, E083491, E083492, E083493, E083499, E083511, E083512, E083513, E083519, E083521, E083522, E083523, E083529, E083531, E083532, E083533, E083539, E083541, E083542, E083543, E083549, E083551, E083552, E083553, E083559, E083591, E083592, E083593, E083599, E0836, E0840, E0842, E09311, E09319, E093211, E093212, E093213, E093219, E093291, E093292, E093293, E093299, E093311, E093312, E093313, E093319, E093391, E093392, E093393, E093399, E093411, E093412, E093413, E093419, E093491, E093492, E093493, E093499, E093511, E093512, E093513, E093519, E093521, E093522, E093523, E093529, E093531, E093532, E093533, E093539, E093541, E093542, E093543, E093549, E093551, E093552, E093553, E093559, E093591, E093592, E093593, E093599, E0936, E0940, E0942, E1010, E1011, E1021, E1022, E1029, E10311, E10319, E103211, E103212, E103213, E103219, E103291, E103292, E103293, E103299, E103311, E103312, E103313, E103319, E103391, E103392, E103393, E103399, E103411,

CHADS ₂	Point	ICD-9 Codes	ICD-10 Codes

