			E103412, E103413, E103419, E103491, E103492, E103493, E103499, E103511, E103512, E103513, E103519, E103521, E103522, E103523, E103529, E103531, E103532, E103533, E103539, E103541, E103542, E103543, E103549, E103551, E103552, E103553, E103559, E103591, E103592, E103593, E103599, E1036, E1037X1, E1037X2, E1037X3, E1037X9, E1039, E1040, E1041, E1042, E1043, E1044, E1049, E1051, E1052, E1059, E10610, E10618, E10620, E10621, E10622, E10628, E10630, E10638, E10641, E10649, E1065, E1069, E108, E109, E1100, E1101, E1121, E1122, E1129, E11311, E11319, E113211, E113212, E113213, E113219, E113291, E113292, E113293, E113299, E113311, E113312, E113313, E113319, E113391, E113392, E113393, E113399, E113411, E113412, E113413, E113419, E113491, E113492, E113493, E113499, E113511, E113512, E113513, E113519, E113521, E113522, E113523, E113529, E113531, E113532, E113533, E113539, E113541, E113542, E113543, E113549, E113551, E113552, E113553, E113559, E113591, E113592, E113593, E113599, E1136, E1137X1, E1137X2, E1137X3, E1137X9, E1139, E1140, E1141, E1142, E1143, E1144, E1149, E1151, E1152, E1159, E11610, E11618, E11620, E11621, E11622, E11628, E11630, E11638, E11641, E11649, E1165, E1169, E118, E119, E1300, E1301, E1310, E1311, E1321, E1322, E1329, E13311, E13319, E133211, E133212, E133213, E133219, E133291, E133292, E133293, E133299, E133311, E133312, E133313, E133319, E133391, E133392, E133393, E133399, E133411, E133412, E133413, E133419, E133491, E133492, E133493, E133499,

CHADS ₂	Point	ICD-9 Codes	ICD-10 Codes
			E133511, E133512, E133513, E133519, E133521, E133522, E133523, E133529, E133531, E133532, E133533, E133539, E133541, E133542, E133543, E133549, E133551, E133552, E133553, E133559, E133591, E133592, E133593, E133599, E1336, E1337X1, E1337X2, E1337X3, E1337X9, E1339, E1340, E1341, E1342, E1343, E1344, E1349, E1351, E1352, E1359, E13610, E13618, E13620, E13621, E13622, E13628, E13630, E13638, E13641, E13649, E1365, E1369, E138, E139, E0851, E0852, E0951, E0952, E1051, E1052, E1151, E1152, E1351, E1352

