Hypertension	1 point	401.xx-405.xx	I10, I110, I119, I120, I129, I130, I1310, I1311, I132, I150, I151, I152, I158, I159, I160, I161, I169, N262
Abnormal kidney and/or liver function:	1 point each	Kidney: 580.xx-589.xx	B520, E0821, E0822, E0829, E0921, E0922, E0929, M3214, M3215, M3504, N000, N001, N002, N003, N004, N005, N006, N007, N008, N009, N010, N011, N012, N013, N014, N015, N016, N017, N018, N019, N020, N021, N022, N023, N024, N025, N026, N027, N030, N031, N032, N033, N034, N035, N036, N037, N038, N039, N040, N041, N042, N043, N044, N045, N046, N047, N048, N049, N050, N051, N052, N053, N054, N055, N056, N057, N058, N059, N060, N061, N062, N063, N064, N065, N066, N067, N068, N069, N070, N071, N072, N073, N074, N075, N076, N077, N078, N079, N08, N140, N141, N142, N143, N144, N150, N158, N159, N16, N170, N171, N172, N178, N179, N181, N182, N183, N184, N185, N186, N189, N19, N250, N251, N2581, N2589, N259, N261, N269, N270, N271, N279
Age ≥75 years	2	Liver: 570.xx-573.xx	B251, K700, K7010, K7011, K702, K7030, K7031, K7040, K7041, K709, K710, K7110, K7111, K712, K713, K714, K7150, K7151, K716, K717, K718, K719, K7200, K7201, K7210, K7211, K7290, K7291, K730, K731, K732, K738, K739, K740, K741, K742, K743, K744, K745, K7460, K7469, K750, K751, K752, K753, K754, K7581, K7589, K759, K760, K761, K762, K763, K764, K765, K766, K767, K7681, K7689, K769, K77
Stroke	1 point	History of stroke V12.54, 433.xx-436.xx	G450, G451, G452, G458, G459, G460, G461, G462, I6300, I63011, I63012, I63013, I63019, I6302, I63031, I63032, I63033, I63039, I6309, I6310, I63111, I63112,

HAS-BLED	Point	ICD-9 Codes	ICD-10 Codes
			I63113, I63119, I6312, I63131, I63132, I63133, I63139, I6319, I6320, I63211, I63212, I63213, I63219, I6322, I63231, I63232, I63233, I63239, I6329, I6330, I63311, I63312, I63313, I63319, I63321, I63322, I63323, I63329, I63331, I63332, I63333, I63339, I63341, I63342, I63343, I63349, I6339, I6340, I63411, I63412, I63413, I63419, I63421, I63422, I63423, I63429, I63431, I63432, I63433, I63439, I63441, I63442, I63443, I63449, I6349, I6350, I63511, I63512, I63513, I63519, I63521, I63522, I63523, I63529, I63531, I63532, I63533, I63539, I63541, I63542, I63543, I63549, I6359, I636, I638, I639, I6501, I6502, I6503, I6509, I651, I6521, I6522, I6523, I6529, I658, I659, I6601, I6602, I6603, I6609, I6611, I6612, I6613, I6619, I6621, I6622, I6623, I6629, I663, I668, I669, I67841, I67848, Z8673

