		E113313, E113319, E113391, E113392, E113393, E113399, E113411, E113412, E113413, E113419, E113491, E113492, E113493, E113499, E113511, E113512, E113513, E113519, E113521, E113522, E113523, E113529, E113531, E113532, E113533, E113539, E113541, E113542, E113543, E113549, E113551, E113552, E113553, E113559, E113591, E113592, E113593, E113599, E1136, E1137X1, E1137X2, E1137X3, E1137X9, E1139, E1140, E1141, E1142, E1143, E1144, E1149, E1151, E1152, E1159, E11610, E11618, E11620, E11621, E11622, E11628, E11630, E11638, E11641, E11649, E1165, E1169, E118, E119, E1300, E1301, E1310, E1311, E1321, E1322, E1329, E13311, E13319, E133211, E133212, E133213, E133219, E133291, E133292, E133293, E133299, E133311, E133312, E133313, E133319, E133391, E133392, E133393, E133399, E133411, E133412, E133413, E133419, E133491, E133492, E133493, E133499, E133511, E133512, E133513, E133519, E133521, E133522, E133523, E133529, E133531, E133532, E133533, E133539, E133541, E133542, E133543, E133549, E133551, E133552, E133553, E133559, E133591, E133592, E133593, E133599, E1336, E1337X1, E1337X2, E1337X3, E1337X9, E1339, E1340, E1341, E1342, E1343, E1344, E1349, E1351, E1352, E1359, E13610, E13618, E13620, E13621, E13622, E13628, E13630, E13638, E13641, E13649, E1365, E1369, E138, E139, E0851, E0852, E0951, E0952, E1051, E1052, E1151, E1152, E1351, E1352, E1359, E13610, E13618, E13620, E13621, E13622, E13628, E13630, E13638, E13641, E13649, E1365, E1369, E138, E139
Hypertension	401.xx -405.xx	I10, I110, I119, I120, I129, I130, I1310, I1311, I132, I150, I151, I152, I158, I159, I160, I161, I169, N262
Renal Disease	582.xx; 583.0x-583.79; 585.xx-586.99; 588.xx	B520, E0821, E0822, E0829, E0921, E0922, E0929, I120, I129, I130, I1310, I1311, I132, M3214, M3215, M3504, N000, N001, N002, N003, N004, N005, N006, N007, N008, N009, N010, N011, N012, N013, N014, N015, N016, N017, N018, N019, N020, N021, N022, N023, N024, N025, N026, N027, N028, N029, N030, N031, N032, N033, N034, N035, N036, N037, N038, N039, N040, N041, N042, N043, N044, N045, N046, N047, N048, N049, N050, N051, N052, N053, N054, N055, N056, N057, N058, N059, N060, N061, N062, N063, N064, N065, N066

Covariates	ICD-9-CM/CPT/HCPCS Codes	ICD-10-CM Codes

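### The ICD-10 kidney lists in Tables 7 and 11 count diabetic kidney codes for secondary diabetes but not the matching type 1, type 2 and other-diabetes codes

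*Combined protocol and SAP*

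**What the plan says.** Section 9.3 (Table 1) makes HAS-BLED a baseline variable scored from Appendix Table 7, and renal disease a baseline comorbidity defined by Appendix Table 11. Both belong to the patient description in Aim 1 (Section 8.1.1).

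In Table 7 the item "Abnormal kidney and/or liver function" gives one point for kidney and one for liver. The ICD-9 kidney definition is "Kidney: 580.xx-589.xx". The ICD-10 definition is a list of 121 codes that begins "B520, E0821, E0822, E0829, E0921, E0922, E0929, M3214, M3215, M3504, N000" and later includes "N179, N181, N182, N183, N184, N185, N186, N189, N19, N250". The Renal Disease cell of Table 11 begins in the same way: "B520, E0821, E0822, E0829, E0921, E0922, E0929, I120, I129".

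The kidney codes for the other diabetes types appear in the diabetes row of Table 5, as "E0942, E1010, E1011, E1021, E1022, E1029, E10311", "E1100, E1101, E1121, E1122, E1129, E11311" and "E1310, E1311, E1321, E1322, E1329, E13311". They recur in the diabetes rows of Tables 6 and 11. They appear in neither kidney cell.

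**The concern.** The endings 21, 22 and 29 mark the kidney complications within each ICD-10 diabetes category. Table 7 accepts them as kidney evidence when the diabetes is due to an underlying condition (E08) or a drug (E09), and ignores them for type 1 (E10), type 2 (E11) and other specified diabetes (E13). The plan gives no reason for the split. It cannot be a rule against combination codes, because the E08 and E09 codes are themselves combination codes, and Table 11 also accepts the hypertensive kidney codes in I12 and I13.

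The study population is obese patients, so leaving out type 2 diabetes while keeping secondary diabetes is hard to defend. At stake are the HAS-BLED distribution and the renal disease percentage in the Aim 1 tables, and the accuracy of two variables that could enter the propensity model.

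**Working it through.** No sample size or power figure is involved. The check is whether codes are on the lists.

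**Step 1. Membership of the 15 diabetic kidney codes (ICD-10).** Inputs are the Table 7 kidney cell, the Table 11 Renal Disease cell and the Table 5 diabetes row.

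| Diabetes category | Codes | Table 7 kidney | Table 11 renal | Table 5 diabetes |
|---|---|---|---|---|
| Underlying condition | E0821, E0822, E0829 | 3 of 3 | 3 of 3 | 0 of 3 |
| Drug-induced | E0921, E0922, E0929 | 3 of 3 | 3 of 3 | 0 of 3 |
| Type 1 | E1021, E1022, E1029 | 0 of 3 | 0 of 3 | 3 of 3 |
| Type 2 | E1121, E1122, E1129 | 0 of 3 | 0 of 3 | 3 of 3 |
| Other specified | E1321, E1322, E1329 | 0 of 3 | 0 of 3 | 3 of 3 |

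The kidney cells hold 6 of 15 and the diabetes row holds the other 9. One family of codes has been divided between two items by type of diabetes. HAS-BLED has no diabetes item, so the nine codes contribute nothing to that score.

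**Step 2. What the lists do to individual patients.** Each row gives all the kidney evidence in that patient's baseline.

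| Baseline codes | HAS-BLED kidney point (Table 7) | Renal flag (Table 11) |
|---|---|---|
| E0821 only | 1 | yes |
| E1121 only | 0 | no |
| E1122 with N183 | 1 | yes |
| 250.4x only (ICD-9) | 0 | no |
| 250.4x with 583.81 (ICD-9) | 1 | no |

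Rows 1 and 2 show the inconsistency. Row 3 shows its limit: any other listed kidney code (N181 to N186, N189, N19, N08, N16, the listed N00 to N07 codes) restores the point and the flag. In Table 11 the I12 and I13 codes set the flag as well.

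Rows 4 and 5 matter for the repair. The ICD-9 kidney cells do not name 250.4x either; Table 10 uses it for complicated diabetes. Table 7's range of 580 to 589 includes 583.81, but the 583 part of Table 11's ICD-9 range ends at 583.79 and leaves it out.

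**Step 3. Size, by assumption only.** Let *d* be the share of patients with diabetes and *k* the share of those whose only kidney evidence is one of the nine codes. The share losing the point is *d* × *k*, and the mean HAS-BLED falls by *d* × *k* × 1 point. Neither input is in the documents. For illustration, take *d* from 0.40 to 0.50 and *k* from 0.02 to 0.06:

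- Low: 0.40 × 0.02 = 0.008, or 0.8% of patients and 0.008 points.
- High: 0.50 × 0.06 = 0.030, or 3.0% of patients and 0.03 points.

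This applies only to patients whose baseline is coded in ICD-10. If every such patient also carries a listed N code, *k* is 0 and so is the effect.

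**The case against.** The strongest reply is that the gap is narrow and that the condition is measured elsewhere. Most of this stands, and it rules out three stronger readings that a reader might infer.

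- *That diabetic nephropathy in general scores no kidney point.* The documents do not support this. The same Table 7 cell awards the point for a long list of N codes, so only patients with no other listed kidney code are missed.
- *That the change from ICD-9 to ICD-10 causes the loss.* This would need two facts about coding practice that the documents do not give: that ICD-9 coders routinely added a code in 580 to 589, and that ICD-10 coders add no N code. On the documents alone, both code sets omit the type 1 and type 2 diabetes-chapter kidney codes. For the pair 250.4x with 583.81 against E1121, Table 11 captures neither.
- *That the omission leaves an imbalance which the 10% standardized-difference check cannot detect.* Table 1 includes creatinine clearance from VA laboratory values, which does not depend on diagnosis codes. The Charlson item for complicated diabetes (Table 10) lists E102, E112 and E132 for two points, and Section 9.7.2 names the Charlson score as a possible covariate for the matching model. The Table 11 diabetes flag contains all nine codes. Section 9.7.1 does not say whether HAS-BLED enters the weighting model.

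The reply does not explain why E0821 counts and E1121 does not. Nor does the Table 11 renal flag make good the loss in Table 7, because it has the same gap.

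**Conclusion.** The inconsistency is real and visible in the text: 6 of 6 secondary-diabetes kidney codes are counted in both cells, and 0 of the 9 matching type 1, type 2 and other-diabetes codes. Patients coded only with one of the nine, and with no other listed kidney code, are under-scored on HAS-BLED and missed by the renal flag.

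The consequence is minor. The number affected is not in the documents; under the assumed shares above it is 0.8% to 3.0% of ICD-10-coded patients, or about 0.01 to 0.03 points on the mean HAS-BLED. The likely effect is a slight understatement of HAS-BLED and of renal disease prevalence in the Aim 1 tables. Little effect on the hazard ratio is expected, provided that creatinine clearance (where a VA value exists) or the Charlson score is among the covariates. This is a code-list correction and does not threaten the primary comparison.

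**What to change.** Add E1021, E1022, E1029, E1121, E1122, E1129, E1321, E1322 and E1329 to the ICD-10 kidney cell of Table 7 and to the ICD-10 Renal Disease cell of Table 11.

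Align the ICD-9 cells in the same step: add 250.4x to both tables, and 583.81 to Table 11. Without this, the ICD-10 additions would create a mismatch between the two coding eras: a patient coded only E1121 would count, and a patient coded only 250.4x would not. With both changes, rows 2, 4 and 5 of the patient table in the working all give one point and a positive flag.

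If the sponsor meant to leave these codes out, the appendix should say why the E08 and E09 codes remain. The two kidney lists differ in other places too (N028 and N029 are in Table 11 but not in Table 7), so one reconciliation can cover everything. It fits the clinical review of the coding strategy already promised in Section 9.8.

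The cost is an edit to four table cells and a rerun of the score and the flag. No new data are needed.

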Bleeding	1 point	Baseline bleeding (Table 12) and 280.xx-286.xx	A985, D500, D508, D509, D510, D511, D512, D513, D518, D519, D520, D521, D528, D529, D530, D531, D532, D538, D539, D550, D551, D552, D553, D558, D559, D560, D561, D562, D563, D565, D568, D569, D5700, D5701, D5702, D571, D5720, D57211, D57212, D57219, D573, D5740, D57411, D57412, D57419, D5780, D57811, D57812, D57819, D580, D581, D582, D588, D589, D590, D591, D592, D593, D594, D595, D596, D598, D599, D600, D601, D608, D609, D6101, D6109, D611, D612, D613, D61810, D61811, D61818, D6182, D6189, D619, D62, D62, D630, D631, D638, D640, D641, D642, D643, D644, D6481, D6489, D649, D65, D66, D67, D680, D681, D682, D68311, D68312, D68318, D6832, D684, D688, D689, D7801, D7802, D7821, D7822, E3601, E3602, E89810, E89811, G9731, G9732,

HAS-BLED	Point	ICD-9 Codes	ICD-10 Codes
			G9751, G9752, H05231, H05232, H05233, H05239, H1130, H1131, H1132, H1133, H2100, H2101, H2102, H2103, H31301, H31302, H31303, H31309, H31311, H31312, H31313, H31319, H31411, H31412, H31413, H31419, H3560, H3561, H3562, H3563, H35731, H35732, H35733, H35739, H4310, H4311, H4312, H4313, H44811, H44812, H44813, H44819, H47021, H47022, H47023, H47029, H59111, H59112, H59113, H59119, H59121, H59122, H59123, H59129, H59311, H59312, H59313, H59319, H59321, H59322, H59323, H59329, H61121, H61122, H61123, H61129, H9521, H9522, H9541, H9542, I312, I6000, I6001, I6002, I6010, I6011, I6012, I602, I6030, I6031, I6032, I604, I6050, I6051, I6052, I606, I607, I608, I609, I610, I611, I612, I613, I614, I615, I616, I618, I619, I6200, I6201, I6202, I6203, I621, I629, I8501, I8511, I97410, I97411, I97418, I9742, I97610, I97611, I97618, I97620, J9561, J9562, J95830, J95831, K2211, K226, K250, K252, K254, K256, K260, K262, K264, K266, K270, K272, K274, K276, K280, K282, K284, K286, K2901, K2921, K2931, K2941, K2951, K2961, K2971, K2981, K2991, K31811, K3182, K5521, K5701, K5711, K5713, K5721, K5731, K5733, K5741, K5751, K5753, K5781, K5791, K5793, K625, K6381, K640, K641, K642, K643, K648, K661, K9161, K9162, K91840, K91841, K920, K921, K922, L7601, L7602, L7621, L7622, M2500, M25011, M25012, M25019, M25021, M25022, M25029, M25031, M25032, M25039, M25041, M25042, M25049, M25051, M25052, M25059, M25061, M25062.

HAS-BLED	Point	ICD-9 Codes	ICD-10 Codes

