			M25069, M25071, M25072, M25073, M25074, M25075, M25076, M2508, M96810, M96811, M96830, M96831, N421, N837, N857, N920, N9961, N9962, N99820, N99821, R040, R041, R042, R0489, R049, R310, R319, R58, R710, S0190XA, S062X0A, S062X1A, S062X2A, S062X3A, S062X4A, S062X5A, S062X6A, S062X7A, S062X8A, S062X9A, S06300A, S06301A, S06302A, S06303A, S06304A, S06305A, S06306A, S06307A, S06308A, S06309A, S06340A, S06341A, S06342A, S06343A, S06344A, S06345A, S06346A, S06347A, S06348A, S06349A, S06350A, S06351A, S06352A, S06353A, S06354A, S06355A, S06356A, S06357A, S06358A, S06359A, S06360A, S06361A, S06362A, S06363A, S06364A, S06365A, S06366A, S06367A, S06368A, S06369A, S064X0A, S064X1A, S064X2A, S064X3A, S064X4A, S064X5A, S064X6A, S064X7A, S064X8A, S064X9A, S065X0A, S065X1A, S065X2A, S065X3A, S065X4A, S065X5A, S065X6A, S065X7A, S065X8A, S065X9A, S066X0A, S066X1A, S066X2A, S066X3A, S066X4A, S066X5A, S066X6A, S066X7A, S066X8A, S066X9A, S06890A, S06891A, S06892A, S06893A, S06894A, S06895A, S06896A, S06897A, S06898A, S06899A, S069X0A, S069X1A, S069X2A, S069X3A, S069X4A, S069X5A, S069X6A, S069X7A, S069X8A, S069X9A, S36112A, S37021A, S37022A, S37029A, T792XXA
Labile INR	Not applicable	Not measurable.	Not applicable
Elderly	1 point for age 65 or older	65+ years	65+ years
Alcohol/ Drug Therapy	1 point	303.xx, 305.0x, V11.3x Antiplatelets administered (abciximab, anagrelide HCL, aspirin, aspirin/dipyridamole,	F1010, F10120, F10129, F1020, F1021, F10220, F10229

HAS-BLED	Point	ICD-9 Codes	ICD-10 Codes
		cilostazol, clopidogrel, dipyridamole, eptifibatide, prasugrel, ticagrelor, ticlopidine, tirofiban) NSAIDs administered (bromfenac, celecoxib, diclofenac, etodolac, fenoprofen, flurbiprofen, ibuprofen, indomethacin, ketoprofen, ketorolac, lansoprazole/naproxen, meclofenamate, mefenamic acid, meloxicam, nabumetone, naproxen, oxaprozin, piroxicam, sulindac, tolmetin)	

Table 8. Baseline Medication List

Mechanism of Action	Drug	
Angiotensin converting enzyme inhibitor	Benazepril, Captopril, Enalapril, Fosinopril, Lisinopril, Moexipril, Perindopril, Quinapril, Ramipril, Trandolapril	
Amiodarone	Amiodarone	
Angiotensin receptor blocker	Azilsartan, Candesartan, Eprosartan, Irbesartan, Losartan, Olmesartan, Telmisartan, Valsartan	
Beta blockers	Acebutolol, Atenolol, Betaxolol, Bisoprolol, Esmolol, Carteolol, Carvedeolol, Labetalol, Levobunolol, Metipranolol, Metoprolol, Nebivolol, Nadolol, Penbutolol, Pinodolol, Propranolol, Sotalol, Timolol,	

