Major Bleeding	Major Gastrointestinal bleeding event	456.0, 456.20, 530.82, 531.0x, 531.2x, 531.4x, 531.6x, 532.0x, 532.2x, 532.4x, 532.6x, 533.0x, 533.2x, 533.4x, 533.6x, 534.0x, 534.2x, 534.4x, 534.6x, 535.01, 535.11, 535.21, 535.31, 535.41, 535.51, 535.61, 537.83, 562.02, 562.03, 562.12, 562.13, 568.81, 569.3, 569.85, 578.x; Procedure Code: 44.43	I8501, I8511, K2211, K226, K250, K252, K254, K256, K260, K262, K264, K266, K270, K272, K274, K276, K280, K282, K284, K286, K2901, K2921, K2931, K2941, K2951, K2961, K2971, K2981, K2991, K31811, K3182, K5521, K5701, K5711, K5713, K5721, K5731, K5733, K5741, K5751, K5753, K5781, K5791, K5793, K625, K6381, K661, K920, K921, K922, K9161, K9162, K91840, K91841
	Major Intracranial Hemorrhage (ICH)	430, 431, 432.0, 432.1, 432.9, 852.0x, 852.2x, 852.4x, 853.0x	I6000, I6001, I6002, I6010, I6011, I6012, I602, I6030, I6031, I6032, I604, I6050, I6051, I6052, I606, I607, I608, I609, I610, I611, I612, I613, I614, I615, I616, I618, I619, I6200, I6201, I6202, I6203, I621, I629, S06340A, S06341A, S06342A, S06343A, S06344A, S06345A, S06346A, S06347A, S06348A, S06349A, S06350A, S06351A, S06352A, S06353A, S06354A, S06355A, S06356A, S06357A, S06358A, S06359A, S06360A, S06361A, S06362A, S06363A, S06364A, S06365A, S06366A, S06367A, S06368A, S06369A, S064X0A, S064X1A, S064X2A, S064X3A, S064X4A, S064X5A, S064X6A, S064X7A, S064X8A, S064X9A, S065X0A, S065X1A, S065X2A, S065X3A, S065X4A, S065X5A, S065X6A, S065X7A, S065X8A, S065X9A, S066X0A, S066X1A, S066X2A, S066X3A, S066X4A, S066X5A, S066X6A, S066X7A, S066X8A, S066X9A
	Major Other hemorrhage	285.1, 360.43, 362.43, 362.81, 363.61, 363.62, 363.72, 364.41, 372.72, 374.81, 376.32, 377.42, 379.23, 423.0x, 596.7x, 599.7x, 602.1x, 620.1, 621.4, 626.2, 626.5, 626.7, 626.8, 626.9, 719.1x, 782.7, 784.7, 784.8, 786.3x, 958.2, 997.02, 998.11; Procedure codes: 99.04	D62, D7801, D7802, D7821, D7822, E3601, E3602, E89810, E89811, G9731, G9732, G9751, G9752, H05231, H05232, H05233, H05239, H1130, H1131, H1132, H1133, H2100, H2101, H2102, H2103, H31301, H31302, H31303, H31309, H31311, H31312, H31313, H31319, H31411, H31412, H31413, H31419, H3560, H3561, H3562, H3563, H35731, H35732, H35733, H35739, H4310, H4311, H4312, H4313, H44811, H44812, H44813, H44819, H47021, H47022, H47023, H47029, H59111, H59112, H59113, H59119, H59121, H59122, H59123, H59129, H59311, H59312, H59313, H59319,

Outcome Variables	ICD-9-CM/Procedure Codes	ICD-10-CM Codes/Procedure Codes

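### Table 7's ICD-10 list for the HAS-BLED bleeding point does not match the Table 12 bleeding definition that its ICD-9 column applies

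*Combined protocol and SAP*

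**What the plan says.** HAS-BLED is a listed baseline variable (Section 9.3, Table 1), scored by the algorithm in appendix Table 7. Baseline clinical characteristics are the subject of Aim 1, a primary objective (Section 8.1.1).

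For the bleeding item, Table 7's ICD-9 column gives a rule: "Baseline bleeding (Table 12) and 280.xx-286.xx". The ICD-10 column gives no rule, only an explicit list. That list contains "K625, K6381, K640, K641, K642, K643, K648, K661" and, later, "R58, R710, S0190XA, S062X0A, S062X1A" and "S06898A, S06899A, S069X0A, S069X1A".

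Table 12's ICD-10 major bleeding lists read differently at the same places. The gastrointestinal list has "K5791, K5793, K625, K6381, K661, K920, K921, K922". In the intracranial hemorrhage list the trauma codes begin at S06340A: "I6203, I621, I629, S06340A, S06341A".

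Table 11 has a separate covariate, history of bleeding, which is defined as identical to the Table 12 outcome and carries none of the added codes.

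**The concern.** The study period, January 2013 to December 2017, uses both code sets, so the two columns of Table 7 should express one definition. They do not, and no text explains a broader ICD-10 version. A patient with the same history can score differently depending on which code set was in use.

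That affects a primary descriptive variable. Section 7 says DOACs have been increasingly preferred over warfarin since their approval. If apixaban initiators therefore fall more often in the ICD-10 part of the period, part of any HAS-BLED difference between the cohorts could be a coding artefact. The baseline table would also carry two prior-bleeding measures, HAS-BLED bleeding and history of bleeding, that diverge for reasons beyond the intended 280-286 extension.

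**Working it through.** **Inputs.** (a) Table 7, bleeding row, ICD-10 diagnosis codes, without the D50-D68 codes that mirror ICD-9 280-286. D62 is kept because Table 12 also lists it. (b) Table 12, the three ICD-10 major bleeding diagnosis lists. (c) Table 12, the ICD-9 major bleeding lists. Procedure codes were not compared.

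**Set comparison of (a) and (b).**

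| | Codes |
|---|---|
| Table 7 list | 344 |
| Table 12 lists | 293 |
| In both | 287 |
| Table 7 only | 344 − 287 = 57 |
| Table 12 only | 293 − 287 = 6 |

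**The 57 surplus codes.**
- Hemorrhoids: K640 to K643 and K648, 5 codes.
- Head injury not specific to hemorrhage: the S062X, S0630, S0689 and S069X blocks, 4 × 10 = 40 codes.
- S0190XA, open head wound: 1 code.
- Others: A985, H61121 to H61123, H61129, N837, R710, S36112A, S37021A, S37022A and S37029A, 11 codes.
- Sum: 5 + 40 + 1 + 11 = 57.

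**The 6 missing codes.** N897, N923, N930, N938, N939 and R233. These work the other way: a patient whose only evidence is one of them loses a point that Table 12 would give.

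**Check against ICD-9.** Table 12's ICD-9 gastrointestinal list starts at 456.0 and has no 455.x code. Its head-trauma codes are 852.0x, .2x and .4x, and 853.0x. Codes 850, 851 and 854 are not bleeding codes there; they fall within the traumatic brain injury ranges used to exclude hemorrhagic stroke cases. The hemorrhoid and non-specific head-injury codes therefore have no ICD-9 route to the point.

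**Size.** Let p be the share of patients coded in ICD-10 whose only listed code is one of the hemorrhoid or non-specific head-injury codes. Each gains 1 point, so their mean HAS-BLED rises by p × 1. The documents give no code frequencies. Purely as an illustration, p between 2% and 6% gives a rise of 0.02 to 0.06 points. If p is the same in both cohorts, the artefact in the cohort difference is p × (ICD-10 share in apixaban − ICD-10 share in warfarin). It cannot exceed p in absolute value, so at most 0.06 points at the top of that range.

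**The case against.** The strongest reply is that this item was never a pure prior-bleeding measure. Its ICD-9 rule includes 280-286, so anemia and coagulation codes score without a bleed in both eras, by design. That is correct. A reader might infer that non-bleeders score only in ICD-10 years, or that the item stops measuring bleeding there. The documents do not support either reading. Only the added codes depend on era, and they matter only for patients with no other listed code.

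A second reply is that no comparative result is shown to be affected. This also stands. Section 9.7.1 leaves the propensity covariates to clinical rationale and does not name HAS-BLED. Prior bleeding can be balanced through the Table 11 covariate, which follows Table 12, and index year is a listed baseline variable. A reader might infer biased weights or hazard ratios; the plan does not establish that.

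Third, a reader might suppose that any routine outpatient hemorrhoid visit scores the point. Section 9.3 says baseline codes count in any position but states no care setting, so this cannot be asserted.

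Fourth, the tables do not label these codes. Reading K64x as hemorrhoids, and the four S06 blocks as not specific to hemorrhage, relies on standard code meaning, and some patients carrying them may have bled. Some of the other 11 codes may denote true bleeding, so deleting every surplus code without review would not be justified.

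None of this explains why the ICD-10 column should differ from the ICD-9 rule. If a broader item was intended, the ICD-9 column would need the same additions.

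**Conclusion.** The mismatch is certain and can be checked code by code: 57 surplus and 6 missing ICD-10 diagnosis codes relative to Table 12. As written, the HAS-BLED bleeding point follows different definitions under the two code sets. The established consequence is an era-dependent distortion in the Aim 1 description of HAS-BLED, one point per affected patient. Its overall size is unknown and probably small: the 2% to 6% range is an assumption, and the documents give neither code frequencies nor the date of the change from ICD-9 to ICD-10. An effect on the weights or hazard ratios would arise only if HAS-BLED were put in the propensity model. The point is worth correcting because the error is definite and the correction nearly free, not because a treatment comparison is shown to be at risk.

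**What to change.** In the ICD-10 cell of Table 7's bleeding row, keep the explicit anemia and coagulation codes as the counterparts of 280-286, and replace the rest with Table 12's ICD-10 major bleeding codes. This removes K640 to K643, K648, the S062X, S0630, S0689 and S069X blocks, and S0190XA, and it restores the six omitted codes. Since Table 12 also lists procedure codes in both code sets, and Table 7's ICD-10 list repeats none, state whether these count.

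Review the other 11 surplus codes (A985, the four H6112x codes, N837, R710, S36112A and the three S3702x codes) individually. If any is kept as a bleeding code, add its ICD-9 counterpart so that both eras use one definition.

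The cost is one code-row edit and a short coding review before programming. No new data are needed.
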